4.1 Recipient Eligibility Criteria

Inclusion Criteria

1. Enrolled in the Recipient Protocol (UMB IRB HP-97730)
2. Provides written informed consent, able to comply with the planned study procedures, be available for an up to ~14-day stay for the CHIVITT and have the ability to attend the scheduled follow-up visits.
3. Subjects must be able to comprehend the study requirements, as evidenced by a score of $\geq 70\%$ or better on the comprehension assessment (two attempts permitted).
4. No significant change (for the worse) in general health history or in concomitant medication use, as compared from their responses collected during screening (EMIT-2 Recipient Protocol).
5. Agree not to meet with other participants (recipients or donors) outside of the programmed exposure events during the course of their participation in the CHIVITT.

Exclusion Criteria

1. Female of childbearing potential who has a positive urine pregnancy test within 24 hours of admission to the hotel quarantine unit or is breastfeeding or planning to become pregnant within 2 months after entry into a CHIVITT.
2. Presence of infection with influenza, SARS-CoV-2, or other respiratory pathogens detected via a multiplex nucleic acid amplification test (e.g., Biofire) at admission to the hotel quarantine facility.
3. Within the past 72 hours, presence of influenza-like illness, as defined as fever of $\geq 100.2^{\circ}\text{F}$ AND cough or sore throat, in the absence of an alternative cause.
4. Receipt of any blood products within the past 2 months.
5. Does not agree to provide permission for secondary research use of extra samples collected and stored specimens.
6. Habitual smoker of tobacco, marijuana, or e-cigarettes per self-report. (*Habitual smokers are those who smoke or vape more than four cigarettes, other tobacco products, e-cigarettes or marijuana in a week for more than three months or use an inhaled nicotine or marijuana product more than 3 days a week on average. Edible or patch forms of tobacco or marijuana products do not constitute an exclusion.*)
7. Self-reported or known history of alcohol or drug abuse in the past two years and/or illicit drug use within the last 30 days. (*Prescribed stimulants for the treatment of ADHD and cannabinoids use do not constitute exclusionary criteria*)
8. Has an ongoing symptomatic condition¹ for which the subject has had or has ongoing medical investigations but has not yet received a diagnosis or treatment plan.
¹*e.g., ongoing chronic fatigue without a diagnosis for symptom.*
9. Presence of self-reported or medically documented significant medical or psychiatric condition(s)²
²*Significant medical or psychiatric conditions include but are not limited to:*
 - a. *Respiratory disease (e.g., chronic obstructive pulmonary disease [COPD], asthma, cystic fibrosis) requiring daily medications* currently or any treatment of respiratory disease exacerbations or hospitalizations for acute respiratory illnesses (e.g., asthma exacerbation) in the last 5 years.*
** Asthma medications: inhaled, oral, or intravenous (IV) corticosteroids, leukotriene modifiers, long and short acting beta agonists, theophylline, ipratropium, biologics.*
 - b. *Significant cardiovascular disease (e.g., congestive heart failure, cardiomyopathy, ischemic heart disease) or history of myocarditis or pericarditis as an adult.*
 - c. *Neurological or neurodevelopmental conditions (e.g., epilepsy, stroke, seizures, encephalopathy, focal neurologic deficits, Guillain-Barré syndrome, encephalomyelitis or transverse myelitis).*
 - d. *Ongoing malignancy or recent diagnosis of malignancy, including leukemia; treated, non-melanoma skin cancers are permissible.*
 - e. *An autoimmune disease.*
 - f. *An immunodeficiency of any cause.*
 - g. *A blood disorder (e.g., sickle cell disease)*
 - h. *Endocrine disorders (e.g., diabetes)*

- i. Liver, kidney, metabolic disorders
- j. $BMI \geq 40 \text{ kg/m}^2$
- k. Any other condition or behavior that in the opinion of the PI would affect the ability to participate in the screening or future transmission studies.

10. Presence of immunosuppression or any medications that may be associated with impaired immune responsiveness³.

³*Including, but not limited to, corticosteroids exceeding 10 mg/day of prednisone equivalent, immunoglobulin, interferon, immunomodulators, cytotoxic drugs, or systemic corticosteroids or other similar or toxic drugs during the preceding 2-month period. Low dose topical and intranasal steroid preparations used for a discrete period are permitted.*

11. Known allergy or intolerance to treatments for influenza and other respiratory infections (including but not limited to oseltamivir, baloxavir, acetaminophen/paracetamol).

12. History of a previous severe allergic reaction to medicines of any kind with generalized urticaria, angioedema, or anaphylaxis.

13. Participating in any other interventional clinical trial that has a scheduled intervention 30 days prior to the start of the CHIVITT or 30 after discharge from the research quarantine unit.

5 CHIVITT OBJECTIVES

Table: Objectives and Endpoints (Outcome Measures)

Objectives	Endpoints (Outcome Measures)
Primary	

 • To determine the relative contribution of the various modes of transmission 	
 • SAR of influenza infection will be determined through virological confirmation, symptomatic infection, or serological evidence
Secondary	

 • To measure influenza viral parameters in Donors and Recipients • To measure influenza illness parameters in Donors and Recipients to assess the impact of aerosol exposure to influenza on disease severity • To evaluate the role of serologic antibody levels on influenza transmission, susceptibility, and immunologic response to infection 	
 • Incidence, duration, and quantity of virus shedding in donors and recipients • Disease severity parameters in donors and recipients • HAI, NI, and FRNT titers, HA/NA anti-stalk ELISA, and ADCC reporter assays. • Measurement and modeling of aerosol size, virus number per aerosol particle,

• To estimate the infective dose of influenza virus	deposition and environmental dispersion characteristics, and rate of shedding
Exploratory	

 To evaluate the role of mucosal antibody and cellular immunity in transmission and susceptibility. To characterize the quantum of airborne influenza infection and extend models of aerosol inhalation risk from well-mixed to non-well mixed conditions and the personal breathing zone. 	
 Potential assays include IgA in nasal secretions and collection and analysis of cellular immune markers. Exhaled breath viral loads and ambient viral concentrations, environmental parameters, video analysis of individual movement and interpersonal proximity and behaviors.

6 CHIVITT STUDY DESIGN

Each CHIVITT is planned to be conducted with discrete cohorts of Recipients and Donors. The size of each cohort and numbers of Recipients and Donors will vary from cohort to cohort, but the general size of a cohort may consist of up to 20 Recipients and up to 5 Donors per CHIVITT, which would span an approximate 2-week period. The number of Recipients will be determined by each individual's availability and whether their most recent serum antibodies have demonstrated a relative low titer against the influenza virus to be transmitted in the CHIVITT. To maintain the size of the recipient group, we may consider bringing in new recipients during the quarantine study if a significant number of original recipients are infected on the same day. The number of Donors will be determined by the number of participants which are identified with acute symptomatic influenza infection during the time of a CHIVITT cohort's stay.

The CHIVITT studies are anticipated to occur during the peak of local seasonal influenza transmission (e.g., January and February). Timing of the study will be constrained by the necessity to rent the facility for prespecified calendar dates. It is intended that the local seasonal influenza activity will be closely monitored, including the virus subtypes which are predominantly circulating. During the peak of the local seasonal influenza activity, a cohort of Recipients will be contacted to request their willingness to reside up to ~2 weeks on the quarantine research unit for a CHIVITT. The selection of Recipients from the pool of potential Recipients will be partially determined by the demonstration of low antibody titers against the circulating influenza virus, which has been measured in the past year (under the EMIT-2 Recipient Protocol, UMB IRB HP-97730). Potential Recipients will be given some time (\leq one week) to decide whether to participate and they must complete an IRB-approved consent form for the CHIVITT study.

Meanwhile, during the peak of community-wide local seasonal influenza the study team will be attempting to rapidly identify healthy adults with acute and symptomatic influenza infection for consent to participate as Donors in the CHIVITT cohort. It is intended that there could be multiple Donors identified during a ~2-week period; each of these Donor individuals could be introduced into the CHIVITT cohort in an overlapping or sequential fashion, to provide more opportunities for transmission events.

The success of each CHIVITT cohort will be influenced by the unpredictability of an influenza season, which influenza viruses may be circulating, willingness or availability of Recipients for each cohort, and the ability to identify and consent Donors for each cohort. To mitigate these factors, we will enroll sufficient potential

recipients that only a fraction are needed in any one season, multiple cohorts will be studied each year, and multiple clinical sources will participate in recruiting donors.

6.1 General Outline of Activities During Each CHIVITT Cohort

The CHIVITT is to be conducted as a randomized, open, controlled study. Recipient participants for each cohort will enter the study hotel quarantine facility and be housed in individual hotel rooms. After a two-day run-in period to ensure that Recipients are free of preexisting respiratory infections *Exposure Events* will be held in a specially prepared event room.

Recipient participants of each cohort will be randomized to an intervention group or no intervention (Control Recipients, CR). Before entering their first *Exposure Event* each Intervention Recipients (IR) will be trained on how to comply with the intervention. IRs will be required to wear a lightweight plastic face shield, comply with hand hygiene (i.e., using a hand sanitization product every 15 minutes, plus periodic hand washing with soap and water), and avoid face touching during each planned *exposure event*. The face shield may only be removed after leaving the exposure room to go to the bathroom, for other short comfort breaks, and at mealtimes. In these instances, hand hygiene will be used after removing or replacing the face shield; and Donors will not be present. Hand washing with soap and water will be required before meals. IR will be separated from Donors by more than 6 feet during meals. The exposure room will be supervised by a trained member of the study staff who will monitor to ensure that Intervention Recipients wear the face shield continuously, are separated from Donors at meals, and do not touch their faces. Small sticks (e.g., coffee stirrers) will be provided to allow IRs to scratch their faces.

Exposure events are to occur as controlled (prescribed) activities within the exposure room. Exposure events will extend for up to 15 hours per day when Donors are available and able to participate (e.g., 15 hours 8am to 11pm). Each Recipient will participate in up to 60 hours of *Exposure Events* (e.g., 4 days at 15 hours/day) which may be spread over up to 9 or 10 days. During each *Exposure Event* multiple 1-3 hour group activities will be planned and supervised by trained members of the study staff. The group activities are intended to be entertaining and may consist of participating in a card game, board game, foosball game, karaoke, or other group activity which facilitates crowding, loud talking, etc. for potential influenza transmission.

Meanwhile, the exposure room environment will be regulated to control room temperature, humidity, and air hygiene for each CHIVITT. The overarching design of the EMIT-2 program is the evaluation of the contribution of aerosol inhalation to influenza transmission. In order to evaluate the effect of aerosol inhalation, we may alternate the air quality and cleaning between high and low air hygiene conditions during each quarantine cohort with a wash-out period (for example 2 days). High air hygiene conditions will be those where ventilation, filtration, and/or germicidal UV will achieve effective air exchanges of ≥ 10 air changes per hour (eACH), or >10 liters/second/person, or a mean target CO₂ concentration of ≤ 200 parts per million (ppm) above the outdoor concentration (if high air hygiene is achieved with ventilation alone). Low air hygiene conditions will be those where effective air exchanges will be ≤ 0.7 ACH or <1 liter/second/person (similar to an unventilated dorm room at the University of Maryland College Park), or a mean target CO₂ concentration of $\geq 2,500$ ppm (similar to a poorly ventilated public-school classroom), or as low as achievable while controlling temperature in a comfortable range and relative humidity $<40\%$. It is intended that the first CHIVITT (Year 1) will be performed with the low air hygiene, ventilation, filtration, and no germicidal UV conditions so that we can determine the attack rate of influenza under

the circumstances which will most facilitate inhalation exposure and influenza transmission. In subsequent years, the air hygiene conditions will be alternated within each CHIVITT cohort.

Within the exposure room, digital cameras will be mounted for photography and video recording of the *exposure events*. The photos and video information are used to monitor and characterize the direction of exhaled breath, duration and proximity of persons from each other, and other positional information which will be needed to develop the analytical models of aerosol transmission. Although the content of conversations is not the intent of the recordings, some audio data may be analyzed for “loudness” and audible coughs and sneezes, as a proxy for periods during which higher exhaled breaths may be generated. In some CHIVITTS we may employ newer technologies, such as wearable biosensors with geo-positional data collection to allow for the investigators to collect data on minute respiratory rate, heart rate, and proximity.

When Recipients and Donors are not participating in exposure events, the participants will be separated as much as possible to avoid transmission outside of the exposure events. Anti-septic hand hygiene products will be widely available throughout the area. In-room air filtration and/or germicidal UV fixtures will also be used to decontaminate the air of individual hotel rooms and hallways.

6.2 Duration of Donor Participation

It is intended that symptomatic influenza-infected Donors be introduced into the CHIVITT as soon as possible after onset of symptoms, while still shedding influenza viruses. When the daily influenza testing (e.g., using BioFire Respiratory Panel testing or exhaled breath testing) demonstrates no detectable virus, which is anticipated to occur by approximately 3 to 5 days from the initiation of symptoms, or more than three days has elapsed since onset of symptoms, discharge plans for the participant may be entertained. Safe discharge will be contingent upon the absence of sufficient illness which may require escalation of care ([section 6.8](#)). Donors may also be allowed to withdraw from the study early, for their own personal reasons ([section 6.7](#)).

6.3 Duration of Recipient Participation

Recipients will be requested to be available for participation in a CHIVITT cohort for approximately two contiguous weeks. However, they may voluntarily consent to participate for a longer period. Alternatively, if they join the cohort late to replace a significant number of discharged recipients, they may participate for a shorter period. It is possible that there may be multiple exposure event activities in a single day or there may be days where no exposure event activities are planned (e.g., because there are no donors available with shedding virus). Total time for participation in exposure events will be up to 60 hours over the course of a CHIVITT.

6.4 Recipient Confinement

When Recipients are not engaged in an *exposure event* activity they will be in their designated private room (hotel room which includes private bathroom and shower). While in their private room, they will be allowed to use the amenities available to them, including watching TV and using the WiFi internet. They may engage in their professional work activities (telework) but must understand that their work schedules must be highly flexible given the nature of the timing of Donor availability and the timing of some *exposure events* which will be according to the Donor's symptomatology and ability to engage in prescribed activities. Recipients must understand that they are housed in “isolation” conditions such that they will

not be allowed to ingress and egress from the isolation unit at will. Guests will not be permitted during the Recipient's stay on the isolation unit. Limited personal deliveries may be possible but must be negotiated for approval with the investigators and may not consist of illicit drugs, weapons, or other forms of contraband which could present a hazard to the welfare of the participants or staff members. An exercise room equipped with treadmill and/or stationary bicycle is intended to be provided on the quarantine research unit; use of the exercise room's equipment will be single occupancy with sign-up so that inadvertent transmission events can be minimized from this common use space. All meals are to be provided through the facility's food services and outside food deliveries will not be permitted, unless there is a specific need from a participant which has been authorized by the investigators (e.g., special dietary needs which cannot be accommodated sufficiently by the facility food service).

Recipients will be notified that hallways are monitored by video camera and that leaving their room when not authorized by study personnel will result in a reduction in compensation (i.e., the payment scale will be adjusted for failures of compliance).

Should a recipient become laboratory-confirmed influenza infected (a countable SAR) and have accompanying symptoms during the CHIVITT, then the Recipient may be allowed to continue in the CHIVITT as a Donor. In order to accept the Recipient into the Donor status, the Donor informed consent form must be reviewed and signed by the participant. Recipients who are a countable SAR and do not want to continue in the CHIVITT may be safely discharged, contingent upon the absence of sufficient illness which may require treatment of influenza ([section 6.6](#)). However, once the 2 weeks have transpired, and if they have not become influenza infected, they will be allowed to end their participation in the CHIVITT. Recipients will also be allowed to withdraw from the study early, for their own personal reasons (see [section 6.7](#)).

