6.6 Treatment of Influenza

For the healthy young adult, influenza infection is largely a self-limiting viral infection which only requires rest and supportive care. No later than 72 hours of a Recipient demonstrating any criteria which satisfy the primary outcome of SAR influenza infection and immediately upon onset of fever $>102^{\circ}\text{F}$, meeting other criteria for a grade 3 adverse event (see Appendix A), or as required by the clinical judgement of study physicians, therapeutic intervention with an approved influenza antiviral agent (i.e., oseltamivir or baloxavir marboxil) will commence. Meanwhile, the subject will be requested to provide exhaled breath specimens; the subject will not be required to participate in additional *exposure event* group activities.

Recipients that become secondarily influenza infected may provide voluntary consent to continue in the CHIVITT as a Donor; the Donor consent form must be reviewed and signed in order for the participant to

continue as a Donor. Under this circumstance, treatment with the influenza antiviral agent will be withheld and the subject (now considered an infectious subject) will be instructed to participate in *exposure event* group activities, as a Donor participant. The participant may choose to terminate their participation as a Donor participant at any time before the maximum 5 days, as originally intended for a Donor participant. Upon deciding to terminate in participation in the CHIVITT, the subject can be administered an influenza antiviral agent and may be discharged. Under all circumstances, symptoms of an influenza infection are intended to be followed to resolution and this may be done through phone call contacts upon discharge; the dates of resolution of influenza symptoms are intended to be documented.

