6.8 Escalation of Care

In rare instances a subject's illness may meet criteria for escalation of care, wherein more in-depth evaluation and/or treatment of illness may be necessary. Escalation of care may involve referral to the local Emergency Room or Urgent Care Center, as the investigator has deemed the severity of illness to be beyond the simple supportive care which can be provided by the EMIT-2 facility. Subjects infected with influenza will be monitored for the possible development of severe symptoms and any influenza complications (as outlined in [section 2.5.1](#)). If a subject has a severe influenza complication(s) or has shortness of breath with an $\text{SpO}_2 < 89\%$ or has any 2 severe grade vital signs (see [Appendix A](#) for severity grading for vital signs), then escalation of care is to be considered.

Therapeutic intervention with an approved influenza antiviral agent (oseltamivir or baloxavir marboxil) should commence immediately upon recognition that escalation of care for influenza is necessary and if not yet already initiated. Study physicians have the authority to exercise clinical judgement to initiate referral for pulmonary function testing, chest radiography, institution of supplemental oxygen, or the initiation of bronchodilators for management. Escalation of care may also include immediate referral to the local urgent care or emergency department for rapid diagnostic testing and/or management. The intent is that there will be no delay in providing appropriate escalation of care to study participants and that the study physicians document their decision-making process. UMB and/or its affiliated institutions or healthcare groups will not provide financial compensation or reimbursement for the cost of referred care that may be provided. The institution or group providing medical treatment will charge the participant's insurance carrier.

Meanwhile, the ill subject will not be required to participate in *exposure event* group activities and will be afforded the time to rest and recover or be referred for higher-level care. Participant preference is intended to be honored. However, when the investigator judges that escalation of care is necessary for the welfare of the participant then participation in *exposure event* activities will be prohibited.

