- The conditions of each exposure event, time, duration, and which participants engaged in the activity are to be documented in study logs.

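### Recipients who become Donors can carry source load from one air-hygiene period into the next, and the stated model has no term for it

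*Protocol*

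**What the plan says.** **Conversion.** Section 6.4 provides that if a Recipient is laboratory-confirmed and symptomatic, "then the Recipient may be allowed to continue in the CHIVITT as a Donor", after signing the Donor consent. Section 6.6 adds that "treatment with the influenza antiviral agent will be withheld and the subject (now considered an infectious subject) will be instructed to participate in" exposure events as a Donor. The role can be ended "at any time before the maximum 5 days, as originally intended for a Donor participant".

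**Alternation.** Section 6.1 says "we may alternate the air quality and cleaning between high and low air hygiene conditions during each quarantine cohort with a wash-out period", giving 2 days as an example. Year 1 is planned as low air hygiene only. After that: "In subsequent years, the air hygiene conditions will be alternated within each CHIVITT cohort". Section 8.1.2 randomises Intervention Recipients (IR) against Control Recipients (CR) within each event. No randomised or balanced order of air-hygiene conditions is stated.

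**Timing and size.** Section 2.5.1 gives a 24-48 hour incubation. Section 2.3 ties the SAR of about 25% to up to 60 cumulative hours per Recipient, and Section 6.3 caps exposure at 60 hours per CHIVITT. Section 6 allows up to 20 Recipients and 5 Donors per cohort.

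**Analysis.** Section 9.3 uses a logistic GEE with the cohort as cluster. The interventions are treated as independent and the model adjusts for sex, race-ethnicity and age.

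**Infected Recipients who are not Donors.** Section 6.6 says "the subject will not be required to participate in additional" exposure events. Section 6.8 does prohibit attendance, but only "when the investigator judges that escalation of care is necessary for the welfare of the participant then participation in" exposure events would be at issue.

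**The concern.** A person infected late in one air-hygiene period becomes symptomatic during or just after a 2-day wash-out. That person may then attend events as an untreated Donor for longer than the wash-out lasts. The number of such Donors is an outcome of the period just finished: more of them are expected after low air hygiene than after high.

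The exposure in the second period is therefore partly caused by the first condition. A GEE working correlation deals with dependence between cohort members when standard errors are computed. It does not remove a difference in exposure that the earlier condition produced.

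At stake is the comparison that answers the primary question, the contribution of aerosol inhalation. If low precedes high, the high-hygiene period has extra sources and the airborne contribution is understated. If high precedes low, it is slightly overstated.

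**Working it through.** **1. The plan's own figure.** Section 9.2 assumes an SAR of 25% and a 79% reduction, that is 25% × 0.21 = 5.25%. With 54 per group (equal control group assumed), one-sided alpha of 5% and a continuity-corrected normal approximation, power is 83.9%, which reproduces the stated 84%. That calculation takes the source load as equal under both conditions.

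**2. Does the wash-out break the link?** Infection at the end of period 1, plus 24-48 hours of incubation, gives symptom onset at or before the end of a 2-day wash-out. The Donor role may last up to 5 days. So it does not.

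**3. Illustration of size.**

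From the protocol: 25% SAR over up to 60 hours; 79% reduction for air hygiene; 76% reduction for shield and hand hygiene (25% × 0.24 = 6%); 20 Recipients.

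Assumed: two periods of equal length within the 60 hours; 10 CR and 10 IR; 2.5 external Donors per period; hazard proportional to the number of sources; a share k of infected Recipients acting as sources throughout the next period.

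Per-period risks with external Donors only:
- Low, CR: 1 − 0.75^0.5 = 13.4%
- Low, IR: 1 − 0.94^0.5 = 3.05%
- High, CR: 1 − 0.9475^0.5 = 2.66%
- True per-period reduction in CR: 1 − 2.66/13.4 = 80%

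Infected in a low period: 10 × 0.134 + 10 × 0.0305 = 1.64.

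*Low then high.* The source multiplier is m = (2.5 + k × 1.64)/2.5. The high-period CR risk is 1 − 0.9475^(0.5m). The apparent reduction is 1 − risk/13.4%.

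| k | m | High-period CR risk | Apparent reduction |
|---|---|---|---|
| 25% | 1.16 | 3.09% | 77% |
| 50% | 1.33 | 3.52% | 74% |
| 100% | 1.66 | 4.37% | 67% |

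*High then low, k = 50%.* With the 76% effect also applied under high hygiene, the IR risk over 60 hours is 5.25% × 0.24 = 1.26%, or 0.63% per period. Infected: 10 × 0.0266 + 10 × 0.0063 = 0.33. Then m = (2.5 + 0.5 × 0.33)/2.5 = 1.07, the low-period CR risk is 1 − 0.75^(0.5 × 1.066) = 14.2%, and the apparent reduction is 1 − 2.66/14.2 = 81%.

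*Balanced orders, k = 50%.* The mean low risk is (13.4 + 14.2)/2 = 13.8% and the mean high risk is (2.66 + 3.52)/2 = 3.09%. The apparent reduction is 1 − 3.09/13.8 = 78%.

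**4. What is not affected.** Year 1 has one air condition. IR and CR at the same event share the same sources, so that contrast is largely protected.

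**The case against.** **Size.** A reader might place the full 25% SAR in a single low-hygiene period. That gives 10 × 0.25 + 10 × 0.06 = 3.1 infected and multipliers of 1.31, 1.62 and 2.24. High-hygiene risks are then 6.8%, 8.4% and 11.4%, so 79% would appear as about 73%, 67% and 54%. Sections 2.3 and 6.3 do not support this: the 25% belongs to up to 60 cumulative hours over the whole CHIVITT. Splitting the hours roughly halves the bias.

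Even the smaller figures may be high. Early cases can convert within the same period and raise its own risk. Conversion also needs consent and acceptance. Section 6.2 lets discharge be considered more than three days after symptom onset, so the wash-out uses up part of a Donor's time. k = 100% is an outer bound.

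**Infected non-Donors.** A reader might infer that infected Recipients keep attending events as unlogged sources and so spoil the infective-dose estimate. The documents do not say this. Section 8.1.2 requires that "which participants engaged in the activity are to be documented in study logs". Sections 8.1.3, 8.1.4 and 8.4 provide for daily influenza testing after exposure and breath sampling of infected Recipients, and Section 8.5 adds environmental and personal sampling. Sections 6.4 and 6.9 describe discharge for cases who do not wish to be Donors. What remains is a wording gap between not required and prohibited. In addition, Section 6.4 makes symptoms a condition for conversion, while Section 6.6 states conversion without that condition.

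**Left to a SAP.** Covariates are often specified in an SAP, which is not shown. But conversion and alternation are fixed in this protocol, and Section 9.3 does name the adjustment set.

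The formal Donor route across an air-hygiene switch stands.

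**Conclusion.** The point holds for formal conversion. Nothing in the stated design or model stops the source load in one period from depending on the previous air condition. Direction depends on order, which the protocol does not fix. In the illustration, a true reduction of about 80% appears as 77%, 74% or 67% in low-then-high order, 81% in high-then-low order at k = 50%, and 78% with balanced orders at k = 50%.

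These figures rest on equal periods, 2.5 external Donors per period, proportional hazard and the chosen values of k, none of which the protocol gives. They show a moderate bias in the primary air-hygiene contrast that is cheap to reduce. They do not show that the contrast is invalid. Balancing the order limits the bias but still leaves some dilution of a real effect.

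**What to change.** 1. In Section 9.3, compute Donor-hours per exposure event from the logs already required by Section 8.1.2, split into external and Recipient-derived. Include source load and period in the air-hygiene comparison.
2. State that the order of air-hygiene conditions will be balanced or randomised across cohorts.
3. Report a sensitivity analysis limited to exposure before the first Recipient-derived Donor entered.
4. Separately, reconcile Sections 6.4, 6.6 and 6.8 on whether an infected Recipient who is not a Donor may attend exposure events, and Sections 6.4 and 6.6 on the condition for conversion.

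The cost is some extra analysis, advance planning of the order, and lower precision in the sensitivity analysis, which may keep little high-hygiene exposure in low-first cohorts. Barring Recipient-derived Donors from crossing a switch is not recommended here: it would give up Donor time when Section 6 already calls the influenza season and Donor recruitment uncertain.
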